8.3 Safety assessments

Safety assessments will consist of monitoring and recording all adverse events and serious adverse events, the regular monitoring of hematology and blood chemistry, pregnancy testing (in women of childbearing potential), regular measurement of vital signs, and the performance of physical/neurological examinations; ECGs and other cardiac monitoring may be performed as necessary.

8.4 Quality Assurance

Neuropathology: The neuropathologic diagnosis of glioblastoma will be made at the respective institution. If any question arises regarding the accuracy of the neuropathologic diagnosis, slides (and pathological blocks, if necessary) will be reviewed by the central review pathologist. For protocols with “response” as an outcome, all patients with a documented complete response or partial response may have representative pathology slides undergo central review.

Neuroradiology: MRI scans of patients showing tumor response as assessed locally will be centrally reviewed by the ABTC Imaging Core at the UCLA Brain Tumor Imaging Laboratory by board-certified neuroradiologists who will independently assess tumor size and assess radiographic response.

Adherence to protocol therapy: Screening/baseline source documentation will be submitted/uploaded into CTEP’s iMedidata Rave system and will be reviewed by the ABTC Central Office. As a quality assurance measure for the treatment delivered on this protocol, primary patient records may be reviewed. The records to be examined will be selected retrospectively and at random; complete records must therefore be maintained on each patient treated on the protocol. These records should include primary documentation (e.g., laboratory report slips, X-ray reports, scan reports, pathology reports, physician notes, etc.), which confirm that:

- The patient met each eligibility criterion.
- Signed informed consent was obtained prior to treatment.
- Treatment was given according to protocol (dated notes about doses given; any reasons for any dose modifications).
- Toxicity was assessed according to protocol (laboratory report slips, etc.).
- Response was assessed according to protocol (MRI scan, lab reports, dated notes on measurements and clinical assessment, as appropriate).
- NCI Drug Accountability Records were maintained for this protocol.

9.0 MONITORING OF PATIENTS

9.1 Table of Required Observations

PT2385 (28-Day Cycles)

	Baseline	Days 1-28 of every cycle	Cycle 1	Weekly During Cycle 1	Weekly During All Cycles	Pre-Odd Cycles (cycles 3+)	Pre-Even Cycles	Off Treatment	30 Days post-last dose
PT2385		6							
Glucocorticoids Dose Evaluation	1					5		8	
AE Evaluation	1			7		5	5	8,10	11
MRI	1,15					5		8	
H&P/Neuro Exam	1					5	5	8	
KPS	1					5	5	8	
Vital Signs with pulse oximetry	1,2			2,7		2,5	2,5	2,8	
CBC, Diff, Platelets	1				9,7	5,9	5,9	8	
Serum Chemistry	1,3			3,7		3,5	3,5	3,8	
APTT or PTT	1								
Serum Pregnancy Test	1,4								

Plasma Samples for Pharmacokinetics			12						
Plasma Samples for Pharmacodynamics			13						
Plasma Sample for Pharmacogenomics	14								
Archived Tumor Tissue	16								

- 1– All baseline measurements must be done within minus 21 calendar days of treatment administration unless otherwise specified.
- 2– Including blood pressure, respiratory rate, heart rate, temperature, weight, height: height is required at baseline only; weight is required at pre-odd cycle evaluations only. Patients with dyspnea or asymptomatic desaturation (oxygen saturation <92%), will be further evaluated as clinically indicated: evaluation may include chest x-ray, arterial blood gas analysis, pulmonary function testing including diffusion capacity, co-oximetry, as well as evaluation for specific causes of hypoxia/dyspnea.
- 3– Including albumin, alkaline phosphatase, total bilirubin, calcium, creatinine, magnesium, phosphorus, potassium, SGOT, SGPT, sodium.
- 4– For women of child-bearing potential.
- 5– Within minus 5 calendar days of cycle start.
- 6– PT2385 is administered orally twice daily on Days 1-28 of each 28-day cycle (see Section [4.3.1](#)). Patients are required to keep a medication diary. 7– ± 1 day
- 8– Evaluations done within +7 days of off treatment date unless indicated: do not repeat: if MRI within minus 14 days of off-treatment date; if H&P/neuro, KPS, labs within minus 5 days of off-treatment date.
- 9– If ANC < 1500 or plts < 100,000, CBCs/differentials will be repeated twice a week until counts are recovered (ANC ≥1500 or plts ≥100,000) per protocol. If counts are recovered (ANC ≥1500 or plts ≥100,000) on day of scheduled drawing do not repeat until next protocol schedule day
- 10 – Adverse Events must be followed for at least 30 days from last dose of PT2385.
- 11– Perform within +14 days of the 30-day post-last dose date.
- 12– Plasma samples will be obtained for pharmacokinetics in Cycle 1 at Weeks 1, 2, and 4; see Section [9.5.1](#) for details.
- 13– Plasma samples will be obtained for pharmacodynamics in Cycle 1 at Weeks 1 and 4; see Section [9.5.2](#) for details.
- 14– A single whole blood sample will be collected at baseline for pharmacogenomics. See Section [9.5.3](#).
- 15– Baseline MRI at qualified sites will also include advanced MR imaging measurements in addition to standard anatomic sequences. See Section [9.5.4](#).
- 16– Archived tumor tissue from the most recent resection for glioblastoma will be collected from patients when sufficient tissue is available. See Section [9.5.5](#).

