3.2 Eligibility Criteria

1. Patients must have histologically confirmed glioblastoma that is progressive or recurrent following radiation therapy and temozolomide according to the Response Assessment in Neuro-Oncology (RANO) criteria with:
 - a) New contrast-enhancing lesion outside of radiation field on decreasing, stable, or increasing doses of corticosteroids.
 - b) Increase by $\geq 25\%$ in the sum of the products of perpendicular diameters between the postradiotherapy scan with the smallest tumor measurement and a scan at least 12 weeks from completion of RT+TMZ, on stable or increasing doses of corticosteroids.

Note: clinical deterioration not attributable to concurrent medication or comorbid conditions is sufficient to declare progression on current treatment but not for entry onto a clinical trial for recurrence.

2. Tumor O(6)-methylguanine-DNA-methyltransferase (MGMT) methylation status must be available. Results of routinely used methods for MGMT methylation testing (e.g. methylation-specific polymerase chain reaction, MSPCR, or quantitative PCR) are acceptable.

3. Patients must have a tumor tissue form indicating availability of archived tissue from a previous surgery for glioblastoma, completed and signed by a pathologist. See Section [9.5.5](#).
4. Patients must have measurable (defined by at least 1 cm x 1 cm) contrast-enhancing disease by MRI imaging within 21 days of starting treatment.
5. Patients must be able to undergo MRI of the brain with gadolinium. Patients must be maintained on a stable or decreasing dose of corticosteroid regimen (no increase for 5 days) prior to this baseline MRI.
6. Patients must be in first recurrence of glioblastoma following radiation therapy and temozolomide.
7. Patients must have recovered from severe toxicity of prior therapy. The following intervals from previous treatments are required to be eligible:
 - 12 weeks from the completion of radiation.
 - 6 weeks from a nitrosourea chemotherapy
 - 3 weeks from a non-nitrosourea chemotherapy
 - 4 weeks from any investigational (not FDA-approved) agents
 - 2 weeks from administration of a non-cytotoxic, FDA-approved agent (e.g., erlotinib, hydroxychloroquine, etc.)
8. Patients must be 18 years of age or older.
9. Patients must have a Karnofsky Performance (KPS) Status \geq 60% (i.e. the patient must be able to care for himself/herself with occasional help from others).
10. Patients must have the following organ and marrow function:

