Absolute neutrophil count	\geq 1,500/mcL
Platelets	\geq 100,000/mcL
Hemoglobin	\geq 9 g/dL
Total bilirubin	\leq institutional upper limit of normal
AST (SGOT)/ALT (SGPT)	\leq 4 \times institutional upper limit of normal
Creatinine	\leq institutional upper limit of normal
OR	
Creatinine clearance	\geq 60 ml/min/1.73m ² for patients with creatinine levels above institutional normal
APTT or PTT	\leq 1.5 x institutional upper limit of normal

11. Patients must be able to provide written informed consent.
12. Women of childbearing potential must have a negative serum pregnancy test prior to study start. Women of childbearing potential and men must agree to use adequate contraception (hormonal or barrier method of birth control; abstinence) prior to study entry, for the duration of study participation, and through 30 days after the last dose of study drug. Should a woman become pregnant or suspect she is pregnant while participating in this study, she should inform her treating physician immediately. Men treated or enrolled on this protocol must also agree to use adequate contraception prior to the study, for the duration of study participation, and through 30 days after the last dose of study drug.
13. Patients must have no concurrent malignancy except curatively treated basal or squamous cell carcinoma of the skin or carcinoma in situ of the cervix, breast, or bladder. Patients with prior malignancies must be disease-free for \geq five years.
14. Patients must be able to swallow tablets.

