4.2 Treatment Requirements

All eligible patients who consent to this study must have a baseline (post-operative, if surgery is applicable) pre-treatment MRI showing measurable disease (i.e. 1 cm x 1 cm enhancement). This baseline scan must be done within 21 days prior to the initiation of treatment.

Prior to every cycle patients must have:

1) ANC \geq 1500/ μ l and platelets \geq 100,000 / μ l.

AND

2) All toxicities recovered to \leq grade 1 (or tolerable grade 2 for non-hematologic toxicity) or \leq baseline.

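### The last required blood count and toxicity check before Cycle 1 may be 21 days old, against 5 days before every later cycle: a minor safety-scheduling gap with a cheap remedy

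*Combined protocol and SAP*

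**What the plan says.** Section 4.2 of the protocol opens its start criteria with "Prior to every cycle patients must have". It then asks for ANC of at least 1,500/µL, platelets of at least 100,000/µL, and toxicities recovered to grade 1 or less, tolerable grade 2 if non-haematologic, or baseline. Cycle 1 is included. No test date or window is given.

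Timing is set in the Section 9.1 table:

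- **Baseline column, footnote 1:** "All baseline measurements must be done within minus 21 calendar days of treatment administration unless otherwise specified". The baseline cells for CBC, AE Evaluation and Serum Chemistry carry no shorter window.
- **Pre-even and pre-odd columns, footnote 5:** "Within minus 5 calendar days of cycle start". The odd-cycle column starts at Cycle 3, so neither column covers Cycle 1.
- **Weekly checks, footnote 7:** CBC weekly in all cycles, and AE Evaluation and Serum Chemistry weekly in Cycle 1, each ± 1 day.
- **Footnote 9:** when counts are low, "CBCs/differentials will be repeated twice a week until counts are recovered". It is attached to the weekly and pre-cycle CBC cells, not to the baseline cell.

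Section 3.2 item 10 sets the same ANC and platelet limits for eligibility. Item 7 allows entry "3 weeks from a non-nitrosourea chemotherapy". For the MRI, Section 4.2 says: "This baseline scan must be done within 21 days prior to the initiation of treatment".

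**The concern.** One start rule is checked on two different clocks. At Cycle 2 and later, a site that follows the schedule has a count at most 5 days old when it applies Section 4.2. At Cycle 1 it may rely on one that is 21 days old, and the protocol gives no reason for the longer interval.

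What matters before the first dose is late effects of earlier treatment, since the patient has not yet received PT2385. The minimum washout from non-nitrosourea chemotherapy is 3 weeks, the same length as the baseline window. A count can therefore qualify a patient and still have been drawn before a fall caused by that chemotherapy. At stake is a first dose given below the protocol's own start criteria, with the shortfall not seen until the first weekly count. This is a patient-safety and scheduling matter. It has no bearing on the two-stage response design.

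**Working it through.** The plan states no figure on this point, so there is none to reproduce. The check compares the table with Section 4.2 and uses day arithmetic.

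**Inputs**

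- Baseline window: 21 days (9.1, footnote 1)
- Later pre-cycle window: 5 days (9.1, footnote 5)
- Minimum washout, non-nitrosourea chemotherapy: 3 weeks = 21 days (3.2 item 7)
- Weekly check tolerance: ± 1 day (9.1, footnote 7)
- MRI limit: 21 days (4.2)
- Maximum enrolment: 35 (3.1)

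**1. Difference in permitted age of the last check.** 21 − 5 = 16 days.

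**2. Earliest permitted count relative to the last chemotherapy.** Let g be the days from the last non-nitrosourea dose to the first PT2385 dose, with g ≥ 21. The earliest permitted draw is on day g − 21 now, and day g − 5 with a 5-day window.

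| g (days) | Earliest draw now | Earliest draw, 5-day window |
|---|---|---|
| 21 | 0 | 16 |
| 28 | 7 | 23 |
| 35 | 14 | 30 |

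These are permitted dates, not risks. Day 0 is the extreme case.

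**3. Does another provision require a closer check?**

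- Registration (7.0) verifies eligibility within the protocol's timeframes and sets no shorter window for counts.
- The Day 1 pre-dose samples (9.5.1, 9.5.2) are for PK and PD only.
- If the first weekly CBC is read as Day 1, the ± 1 day tolerance lets it fall on Day 2, after dosing has begun.
- If it is read as Day 8 ± 1, it falls 6 to 8 days after the first dose. The longest permitted gap between the baseline count and the next one is then 21 + 7 ± 1 = 27 to 29 days.

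None of these closes the gap.

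**4. What happens to a low count once it is seen?** Section 5.0 modifies dosing for haematologic toxicity attributed to PT2385 only at ANC < 500, platelets < 25,000, febrile neutropenia, or a toxicity that prevents at least 80% of the cycle's planned doses. For events not related to treatment, Section 5.2 calls for delay only at grade 3 or 4, and only if PT2385 may complicate the event. Between those limits and the Section 4.2 thresholds, a low weekly count leads to twice-weekly repeats under footnote 9.

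**5. Room for a delay before the MRI expires.** If the MRI is m days old at planned Day 1, the slack is 21 − m.

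| m (days) | Slack (days) |
|---|---|
| 14 | 7 |
| 18 | 3 |
| 21 | 0 |

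Assuming a twice-weekly repeat means 3 to 4 days, one repeat always fits when 21 − m ≥ 4, that is, m ≤ 17.

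**The case against.** The strongest reply is that the protocol tolerates the state in question. A patient with an ANC a little under 1,500 on the first weekly count would, under Sections 5.0 and 5.2, usually go on dosing with closer monitoring. Missing the same count before dose 1 therefore changes little. This stands, and it removes most of the consequence.

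Two further points also stand. Weekly counts would reveal a fall within about 8 days of the first dose. In addition, neutropenia and thrombocytopenia are not among the most common grade 3/4 events that Section 9.2.1 lists for PT2385 monotherapy.

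It can also be said that the two windows do different jobs: 21 days for screening before any exposure, 5 days for toxicity between cycles. That explains how the difference arose. It does not supply a timed check for a start rule that Section 4.2 expressly applies before every cycle.

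A reader might infer two stronger things that the documents do not support:

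- **That the plan contradicts itself or waives the start criteria for Cycle 1.** It does not. Section 4.2 covers Cycle 1, Section 3.2 item 10 sets the same count limits at baseline, and Section 3.3 item 6 excludes patients with unrecovered toxicity from prior therapy. A patient known to be below the limits may not start, and a site is free to retest. The gap is confined to a fall that follows a qualifying result and goes unseen.
- **That patients are likely to start treatment with dangerous cytopenia.** The documents give no rate for such falls. The day-0 case needs both the earliest possible draw and the shortest possible washout.

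**Conclusion.** The gap is real and minor. At first dose the last required CBC, AE check and serum chemistry may be 21 days old, 16 days older than at any later cycle, and no other provision requires a closer one. A patient could take dose 1 below the Section 4.2 criteria until the first weekly count, at the latest about Day 8 ± 1.

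The number of patients this would affect cannot be derived from the documents; the only bounds are 0 and 35. Expected harm is small, for the reasons accepted above. The response endpoint and the two-stage rule are unaffected. This is a low-severity, low-cost improvement and not a flaw in the design.

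The conclusion rests on the table cells as they appear in the extracted text of Section 9.1, and on counting the chemotherapy washout to the first PT2385 dose.

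**What to change.** In Section 9.1, add a pre-Cycle 1 requirement for three rows (CBC/Diff/Platelets, AE Evaluation and Serum Chemistry), for example:

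*To be done no more than 5 calendar days before Cycle 1 Day 1, or at the Day 1 visit with results available before dose 1; reviewed against Section 4.2 before dosing. Not repeated if the baseline results already meet this window.*

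Serum chemistry belongs with the other two rows because Section 4.2 requires recovery of all toxicities, laboratory ones included, and chemistry also tightens to 5 days in later cycles. Keep 21 days for the MRI and the other baseline items, and do not re-apply the full eligibility limits of Section 3.2 item 10.

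**Cost**

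- **Patient who passes:** at most one extra routine blood draw and toxicity check (up to 35 patients), or none if baseline falls within 5 days of Day 1. If done on Day 1, the safety sample must be drawn early enough for results to return. The PK and PD sample, taken within 15 minutes of dosing, is too late for that.
- **Patient who fails:** a delayed first dose with repeat tests, and rarely a repeat MRI if the delay passes the 21-day limit. Section 4.2 already requires that delay; the check makes the need for it visible.
- **Registered patient whose counts never recover:** remains untreated in the intent-to-treat population, which Section 11.0 defines as everyone enrolled. Where practical, drawing the baseline samples before registration and within 5 days of Day 1 limits this and avoids a second draw.

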5.0 DOSING DELAYS/DOSE MODIFICATION FOR TOXICITY

Clinically significant adverse events or abnormal laboratory values assessed as unrelated to disease progression, intercurrent illness, or concomitant medications may require dose delay and/or dose modification. Such toxicities must have an attribution of possible, probable, or definite to PT2385 (see Section [9.2.2](#)). If multiple toxicities occur, dose modification decisions should be based on the most severe toxicity.

For patients experiencing toxicity meeting the criteria below, PT2385 will be stopped. If the patient recovers (\leq grade 1 [or tolerable grade 2 for non-hematologic toxicity] or \leq baseline) a dose reduction is required for subsequent doses. Skipped doses will not be made up. If there is any question or clarification required concerning a toxicity, the treating site should contact the ABTC Central Office to determine patient's toxicity status. The ABTC Central Office, with the Study Chair (who may consult with Peloton Medical), will make the final decision.

- Hematological toxicities will require dose modification if any of the following occur and complete blood counts and differentials were obtained according to the

mandated schedule (CBC, differential, and platelets drawn twice a week until the ANC \geq 1500/ mcL and platelets \geq 100,000/ mcL): grade 3 or 4 lymphopenia will not be considered a toxicity requiring dose modification.

- ANC of $<$ 500/ mcL
- Platelets $<$ 25,000/ mcL
- Febrile neutropenia
- Any hematological toxicity that prevents administration of \geq 80% of the planned PT2385 doses for that cycle

➤ Non-hematological toxicities will require dose modification if any of the following occur:

- Grades 3-4 severity (except nausea, vomiting, and diarrhea without sufficient prophylaxis; except alopecia; except grade 3 hyperglycemia; except grade 3 electrolyte disturbances that are asymptomatic and that respond to replacement therapy; and except grade 3 neurologic toxicity responding within two weeks to steroids, anticonvulsants, or electrolyte correction; and except Grade 3 asymptomatic hypoxia. A subject's first episode of deep venous thrombosis [DVT] or pulmonary embolism [PE] will not require dose modification)

ANY TREATMENT RELATED TOXICITY (AS DEFINED ABOVE) CAUSING DELAY IN TREATMENT OF OVER 21 DAYS IN THE START OF A CYCLE WOULD RESULT IN TAKING THE PATIENT OFF TREATMENT.

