5.1 Dose Modification for PT2385

The dose levels and the general approach to PT2385 dose modification on this trial are shown below. Adverse events (AEs) should be treated with the appropriate maximum supportive care, and dose reductions should be clearly recorded on the case report form.

Dose reductions are required for any clinically significant toxicity as defined above. Dosing will stop until the toxicity has resolved to \leq grade 1 (or tolerable grade 2 for nonhematologic toxicity) or \leq baseline. After resolution, when dose reduction is permitted, the dose of PT2385 will be modified as stipulated below, with a maximum of 2 dose reductions. The maximum length of time that PT2385 can be held is 21 days. If treatment-related toxicity is not resolved in \leq 21 days, the patient will be removed from treatment. If there is any question, the ABTC Central Office and the Study Chair should be contacted. The ABTC Study Chair may consult with Peloton Medical as needed for any issues.

Dose Reduction Table for PT2385

Dose Level	PT2385
Starting dose	800 mg b.i.d.
First dose reduction	600 mg b.i.d.
Second dose reduction	400 mg b.i.d.

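### Footnote 9 of the observation table ends repeat blood counts when ANC or platelets recover, while Section 5.0 requires both; read literally, a single-lineage cytopenia drops back to weekly counts

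*Combined protocol and SAP*

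**What the plan says.** Three places in the combined protocol and SAP use the same two thresholds, ANC 1500 and platelets 100,000.

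- **Section 9.1, footnote 9 (attached to the CBC row).** The trigger is either lineage low: "If ANC < 1500 or plts < 100,000, CBCs/differentials will be repeated twice a week". Stopping is then defined with *or*: "CBCs/differentials will be repeated twice a week until counts are recovered (ANC ≥1500 or plts ≥100,000) per protocol". The next sentence repeats the *or*: "If counts are recovered (ANC ≥1500 or plts ≥100,000) on day of scheduled drawing do not repeat until next protocol schedule day".
- **Section 5.0.** In describing the mandated schedule of counts for judging haematological toxicity, it joins the thresholds with *and*: "CBC, differential, and platelets drawn twice a week until the ANC \geq 1500/ mcL and platelets \geq 100,000/ mcL".
- **Section 4.2.** The condition for starting any cycle also uses *and*: "ANC \geq 1500/ μ l and platelets \geq 100,000 / μ l".

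Apart from footnote 9, the table calls for a CBC weekly in all cycles (±1 day, footnote 7) and before each odd and even cycle.

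**The concern.** Footnote 9 and Section 5.0 answer the same question, when twice-weekly counts may stop, with different conjunctions. Section 4.2 governs cycle start rather than repeat counts, so it supports the *and* rule but is not itself the contradiction.

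Four things are at stake for a site that works from the table.

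- **Missed nadir.** PT2385 is given every day of the cycle. The count limits that require dose modification in Section 5.0 are ANC below 500 and platelets below 25,000. A patient whose ANC is between 500 and 1499, or whose platelets are between 25,000 and 99,999, in mid-cycle does not meet those limits and may stay on drug. The twice-weekly draw is the extra check that would show a further fall.
- **Late dating of recovery.** Section 5.1 states: "The maximum length of time that PT2385 can be held is 21 days". Sparser draws can date recovery later against that limit.
- **An unclear condition for dose modification.** Section 5.0 ties its haematological criteria to counts having been obtained on the mandated schedule. With two versions of that schedule, it is unclear whether the condition has been met.
- **Differences between sites.** The trial is multicentre, so sites could follow different rules, and one following the table literally would deviate from Section 5.0.

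**Working it through.** The plan gives no figure to reproduce. The check is a truth table followed by a count of draws.

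**Inputs.** Trigger: ANC < 1500 or platelets < 100,000 (footnote 9). Stop rule A: ANC ≥ 1500 *or* platelets ≥ 100,000 (footnote 9). Stop rule B: ANC ≥ 1500 *and* platelets ≥ 100,000 (Section 5.0). Routine schedule: weekly, ±1 day (Section 9.1). Cycle length: 28 days. Maximum hold: 21 days (Section 5.1).

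**Step 1: is the stop rule already met at the triggering draw?**

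| ANC | Platelets | Triggered | Stop rule A (or) | Stop rule B (and) |
|---|---|---|---|---|
| low | low | yes | not met | not met |
| low | normal | yes | **met** | not met |
| normal | low | yes | **met** | not met |
| normal | normal | no | met | met |

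Rule A is met at once in 2 of the 3 triggering states; rule B in 0 of 3. Under rule A a patient with both lineages low also leaves the twice-weekly schedule as soon as one of them recovers.

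**Step 2: number of draws if one lineage stays low throughout.**

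- 28-day cycle: 28/7 = 4 draws under rule A (weekly), against 2 × 28/7 = 8 under rule B.
- 21-day hold: 21/7 = 3, against 2 × 21/7 = 6.

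These leave out the CBCs taken before each cycle, which may add a draw under either rule.

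**Step 3: spacing.** Weekly draws are 7 days apart, and up to 7 + 1 + 1 = 9 days if one draw is a day early and the next a day late. Twice-weekly draws are 3 to 4 days apart.

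**Step 4: can the spacing matter against the 21-day limit?** An illustration: suppose a hold begins six days after a weekly draw. The next weekly draws fall on hold days 1, 8, 15 and 22. Recovery on day 17 is first seen on day 22, past the limit. With twice-weekly draws, day 15 is followed by day 18 or 19, and recovery is seen in time. If instead the hold begins at a scheduled draw, weekly draws fall on days 7, 14 and 21. The last of these lands on the limit, so with exact timing no recovery is dated too late.

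**The case against.** The strongest reply is that nobody would read the footnote literally. A rule that starts and cancels itself at the same draw makes no sense, and a count that never fell cannot recover. The natural reading is that whichever lineage was low must come back. That reading gives the same schedule as Section 5.0 in all three triggering states. The footnote also defers to the protocol, Section 5.0 states the full rule, and sites are told to take toxicity questions to the coordinating office.

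The *or* is indeed probably a drafting slip, and the benign reading is available. But the footnote does not state it, the same wording appears twice, and the second occurrence instructs the site not to repeat counts. The table is also where a site would look up its blood-draw schedule.

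Other points stand as limits on size. The draw counts are upper bounds, because they assume a cytopenia lasting the whole cycle or the whole hold. The 9-day gap needs opposite extremes of the window on consecutive draws. The 21-day problem arises only for some timings, and restarting after a hold depends on toxicity grade under Section 5.1, not on footnote 9. Neutropenia and thrombocytopenia are not among the most common grade 3/4 toxicities listed for PT2385 in Sections 2.2 and 9.2.1. Lymphopenia, which is listed, is exempt from dose modification. None of this removes the contradiction between footnote 9 and Section 5.0.

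**Conclusion.** The concern holds. Footnote 9 contradicts Section 5.0 on when twice-weekly counts stop, and taken literally it cancels them at the outset for any single-lineage cytopenia. Sampling intensity is then halved for as long as the cytopenia lasts. This rests on a site applying the footnote as written rather than Section 5.0; under the whichever-was-low reading the schedule does not change.

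The consequence is limited to safety monitoring. Weekly CBCs continue, Section 4.2 still blocks a new cycle until both lineages meet their thresholds, and the response-rate endpoint and sample size are unaffected. Few patients are likely to be affected, though the documents give no basis for a number. This is an internal inconsistency that should be corrected, not a threat to the trial's conclusions.

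**What to change.** In footnote 9, replace *or* with *and* in both recovery parentheses, so that each reads ANC ≥ 1500 and platelets ≥ 100,000. Keep *or* in the trigger, where either low lineage should start the extra counts. Leave Sections 5.0 and 4.2 as they are.

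The cost is one word in two places. Compared with the literal footnote, it means about one more blood count per week of cytopenia, at most 6 − 3 = 3 over a 21-day hold. Compared with Section 5.0 it adds nothing.
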